#### 8.5 Disposal of Data

Anonymised imaging and tissue-derived data, and the results of comparative analyses will be stored on secure University of Edinburgh servers in the Edinburgh Imaging server.

File access is password protected and access is specifically restricted to members of the research group using specific permissions administrated by the University IT team.

All data will be kept for 3 years, after which it will be destroyed by University of Edinburgh-approved methods. All paper files will be kept in the locked filing cabinets in the Chief Investigator's locked office for the same period of time and destroyed fully.

Commented [TS11]: This section requests information on what happens after the retention period and disposal of data

#### 8.6 External Transfer of Data

Data collected or generated by the study (including personal data) will not be transferred to any external individuals or organisations outside of the Sponsoring organisation(s).

#### 8.7 Data Controller

A data controller is an organisation that determines the purposes for which, and the manner in which, any personal data are processed.

The University of Edinburgh and NHS Lothian are joint data controllers along with any other entities involved in delivering the study that may be a data controller in accordance with applicable laws (e.g. the site).

#### 8.8 Data Breaches

Any data breaches will be reported to the University of Edinburgh ([[contact]](mailto:[contact])) and NHS Lothian ([[contact]](mailto:[contact])) Data Protection Officers who will onward report to the relevant authority according to the appropriate timelines if required.

## 9 STATISTICS AND DATA ANALYSIS

### 9.1 SAMPLE SIZE CALCULATION

Patient sample size was established to provide statistical significance in accordance with previous imaging biomarker studies for MRS of 2HG [6].

### 9.2 PROPOSED ANALYSES

Patient histology and immunohistochemistry data (IDH1/2, 1p19q, ATRX, p53 status) will be compared to quantitative MRS data and structural MRI data.

Histological analysis will be performed by pathological team. Imaging data analysis will be performed by the research team using in-house analytic scripts on MATLAB [7], and spectroscopy data will be analysed using FID-A [8] and OSPREY [9] platforms. Statistical analysis of the data will be performed using MATLAB and GraphPad Prism software [10].

## 10 ADVERSE EVENTS

### 10.1 Definitions

Adverse Event (AE): any untoward medical occurrence in a patient or clinical study subject.

Serious Adverse Event (SAE): any untoward and unexpected medical occurrence or effect that:

- Results in death
- Is life-threatening – refers to an event in which the subject was at risk of death at the time of the event; it does not refer to an event which hypothetically might have caused death if it were more severe
- Requires hospitalisation, or prolongation of existing inpatients' hospitalisation
- Results in persistent or significant disability or incapacity
- Is a congenital anomaly or birth defect

Medical judgement should be exercised in deciding whether an AE is serious in other situations. Important AEs that are not immediately life-threatening or do not result in death or hospitalisation but may jeopardise the subject or may require intervention to prevent one of the other outcomes listed in the definition above, should also be considered serious.

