### 10.2 Reporting Procedures

All adverse events should be reported. Depending on the nature of the event the reporting procedures below should be followed. Any questions concerning adverse event reporting should be directed to the Chief Investigator in the first instance.

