#### 10.2.1 Non serious AEs

All such events, whether expected or not, should be recorded.

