#### 10.2.2 Serious AEs

An SAE form should be completed and sent to the Chief Investigator within 24 hours.

All SAEs should be reported to the NRES Committee London - Fulham Research Ethics Committee where in the opinion of the Chief Investigator, the event was:

- 'related', i.e. resulted from the administration of any of the research procedures; and
- 'unexpected', i.e. an event that is not listed in the protocol as an expected occurrence

Reports of related and unexpected SAEs should be submitted within 15 days of the Chief Investigator becoming aware of the event, using the NRES SAE form.

Local investigators should report any SAEs as required by their Local Research Ethics Committee and/or Research & Development Office.

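### The SAE definition in section 10.1 requires unexpectedness, which section 10.2.2 treats as a later test, so the trigger for the 24-hour form is ambiguous

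*Protocol*

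**What the plan says.** Section 10.1 gives two definitions. An adverse event is "any untoward medical occurrence in a patient or clinical study subject", with no condition on expectedness. The next definition adds one: an SAE is "any untoward and unexpected medical occurrence or effect that" leads to death, is life-threatening, or meets another listed criterion. A further sentence lets medical judgement add other events as serious: "Important AEs that are not immediately life-threatening or do not result in death or hospitalisation but may jeopardise the subject" or may need intervention to prevent a listed outcome. That sentence has no expectedness condition.

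Section 10.2 sets the general rule: "All adverse events should be reported. Depending on the nature of the event the reporting procedures below should be followed". Two routes follow.

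- Section 10.2.1, for non-serious events: "All such events, whether expected or not, should be recorded".
- Section 10.2.2, for serious events: "An SAE form should be completed and sent to the Chief Investigator within 24 hours". SAEs that the Chief Investigator considers both related to a research procedure and unexpected go to the ethics committee within 15 days. Here unexpected is explained as "an event that is not listed in the protocol as an expected occurrence".

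**The concern.** Seriousness, relatedness and expectedness answer different questions. Section 10.2.2 keeps them apart: a serious event produces a form, and the Chief Investigator then decides whether it was related and unexpected. Section 10.1 moves one of those later judgements into the definition, where it falls to whoever first sees the event.

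At stake is the rapid notice to the Chief Investigator. If a reporter regards a serious event as expected and applies 10.1 as worded, no SAE form is due within 24 hours. The Chief Investigator's opinion on relatedness is also not called for, because 10.2.2 asks for it only on SAEs. An event caused by a research procedure could miss that review because of a view on expectedness formed before anyone had considered cause.

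**Working it through.** No arithmetic applies, and the protocol states no figure to reproduce. The check sets sections 10.1 to 10.2.2 side by side.

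**Step 1: can both sections hold?** Under 10.1, every event meeting the main definition of an SAE is unexpected. Under 10.2.2, SAEs are divided into those that are unexpected and those that are not. For events under the main definition, the second group is empty and that part of the 10.2.2 test does no work. If instead the 10.2.2 test is meant to separate such events, the definition in 10.1 is too narrow. The two sections describe different schemes.

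**Step 2: which route does each event take?** There are two ways to read the word in 10.1. One is its ordinary clinical sense. The other borrows the meaning in 10.2.2, where only events listed in the protocol are expected; the protocol text contains no such list.

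| Event | 10.1 read in the ordinary sense | 10.1 read with the 10.2.2 meaning |
|---|---|---|
| Meets a listed criterion; reporter thinks it unexpected | SAE; 24-hour form | SAE; 24-hour form |
| Meets a listed criterion; reporter thinks it expected | Not an SAE under the main definition; no 24-hour form | Not listed, so unexpected; SAE; 24-hour form |
| Not serious | Recorded under 10.2.1 | Recorded under 10.2.1 |

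The readings differ only in the second row. Nothing in 10.1 tells the reporter which to use.

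**Step 3: does another sentence catch the second row?**

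- The general rule in 10.2 still requires the event to be reported, but it sets no deadline and sends the reader to the routes below it.
- Section 10.2.1 is headed for non-serious events, so a serious but expected event does not belong there. The phrase that disregards expectedness appears only in that section.
- The medical-judgement sentence in 10.1 is written for situations other than the listed criteria. It can bring in lesser events, expected or not, but does not clearly restore an expected death, life-threatening event or hospitalisation.

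None of the three restores the 24-hour form.

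**Step 4: what follows for the ethics committee?** If one meaning of *unexpected* is used throughout, deleting the word from 10.1 does not change which events reach the committee, because 10.2.2 already requires unexpectedness. A committee report is at risk only if the meanings are mixed: the reporter screens out a related event as expected in the ordinary sense, although under 10.2.2 it would count as unexpected because it is not listed.

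**The case against.** The strongest objection is that the gap may be empty. The only meaning of *unexpected* in the protocol is the one in 10.2.2. Since no occurrences are listed as expected, every serious event is unexpected on that meaning, satisfies 10.1 and takes the 24-hour form. This stands in part: it shows that the exclusion of expected serious events is possible, not established. It does not remove the problem, because 10.1 neither defines the word nor refers forward. If the objection is right, the two words in 10.1 do nothing and can go without loss.

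A reader might infer more than the text supports:

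- *That expected serious events go unreported, so that event counts are incomplete or differ by site.* Section 10.2 requires all adverse events to be reported and directs questions to the Chief Investigator. What may be lost is the 24-hour form and the SAE label, not the event. No objective or endpoint uses SAE counts or compares sites.
- *That the 10.2.2 test cannot work without a list.* It gives a definite answer: with nothing listed, every SAE is unexpected, and every related one goes to the committee.
- *That complications of tumour surgery make the problem frequent.* Surgery here is standard care (sections 6.1 and 13.6), and post-surgical participants are scanned after their operation. Section 10.2.2 ties relatedness to research procedures, and the study's imaging is a single MRI/MRS timepoint (section 3.5). A complication of routine surgery would ordinarily fail the relatedness test whatever its expectedness.

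**Conclusion.** The inconsistency is real. Section 10.1 makes unexpectedness part of being an SAE, and 10.2.2 treats it as a later test on SAEs. The consequence is limited to an ambiguity: a reporter who takes the word in its ordinary sense could withhold the 24-hour form, and with it the Chief Investigator's relatedness judgement, for a death, life-threatening event or hospitalisation considered expected. The event would remain reportable under 10.2 without a deadline.

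This conclusion assumes that a reporter may read 10.1 without importing the 10.2.2 meaning, which the wording allows but does not require. The size cannot be quantified, because the protocol gives no expected rate of serious events. The setting is an observational study of 20 patients imaged once. The primary and secondary endpoints, sample size and analysis are untouched. The correction is worth making because it protects safety reporting at almost no cost.

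**What to change.** In section 10.1, delete *and unexpected* from the SAE definition. Seriousness alone then triggers the 24-hour form, and relatedness and expectedness are judged only by the Chief Investigator under 10.2.2, which can stay as it is.

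The cost is a two-word change and slightly more SAE forms. A list of expected occurrences is not needed for this fix. Adding one would be a separate decision, and it could reduce ethics-committee reporting, because listed events would no longer count as unexpected under 10.2.2.

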### 10.2 Reporting Procedures

All adverse events should be reported. Depending on the nature of the event the reporting procedures below should be followed. Any questions concerning adverse event reporting should be directed to the Chief Investigator in the first instance.

#### 10.2.1 Non serious AEs

All such events, whether expected or not, should be recorded.

#### 10.2.2 Serious AEs

An SAE form should be completed and sent to the Chief Investigator within 24 hours.

All SAEs should be reported to the NRES Committee London - Fulham Research Ethics Committee where in the opinion of the Chief Investigator, the event was:

- 'related', i.e. resulted from the administration of any of the research procedures; and
- 'unexpected', i.e. an event that is not listed in the protocol as an expected occurrence

Reports of related and unexpected SAEs should be submitted within 15 days of the Chief Investigator becoming aware of the event, using the NRES SAE form.

Local investigators should report any SAEs as required by their Local Research Ethics Committee and/or Research & Development Office.

## **11 OVERSIGHT ARRANGEMENTS**

### **11.1 INSPECTION OF RECORDS**

Investigators and institutions involved in the study will permit study related monitoring and audits on behalf of the Sponsor, REC review, and regulatory inspection(s). In the event of audit or monitoring, the Investigator agrees to allow the representatives of the Sponsor direct access to all study records and source documentation. In the event of regulatory inspection, the Investigator agrees to allow inspectors direct access to all study records and source documentation.

### **11.2 STUDY MONITORING AND AUDIT**

The ACCORD Sponsor Representative will assess the study to determine if a study specific risk assessment is required.

If required, a study specific risk assessment will be performed by representatives of the Sponsor(s), ACCORD monitors and the QA group, in accordance with ACCORD governance and sponsorship SOPs. Input will be sought from the Chief Investigator or designee. The outcomes of the risk assessment will form the basis of the monitoring plans and audit plans.

If considered necessary, ACCORD clinical trial monitors, or designees, will perform monitoring activities in accordance with the study monitoring plan. This will involve on-site visits and remote monitoring activities as necessary. ACCORD QA personnel, or designees, will perform study audits in accordance with the study audit plan. This will involve investigator site audits, study management audits and facility (including 3rd parties) audits as necessary (delete where not required).

## **12 GOOD CLINICAL PRACTICE**

### **12.1 ETHICAL CONDUCT**

The study will be conducted in accordance with the principles of the International Conference on Harmonisation Tripartite Guideline for Good Clinical Practice (ICH GCP).

Before the study can commence, all necessary approvals will be obtained and any conditions of approvals will be met.

### **12.2 INVESTIGATOR RESPONSIBILITIES**

The Investigator is responsible for the overall conduct of the study at the site and compliance with the protocol and any protocol amendments. In accordance with the principles of ICH GCP, the following areas listed in this section are also the responsibility of the Investigator. Responsibilities may be delegated to an appropriate member of study site staff.

Delegated tasks must be documented on a Delegation Log and signed by all those named on the list prior to undertaking applicable study-related procedures.

#### **12.2.1 Informed Consent**

The Investigator is responsible for ensuring informed consent is obtained before any study specific procedures are carried out. The decision of a participant to participate in clinical research is voluntary and should be based on a clear understanding of what is involved.

Participants must receive adequate oral and written information – appropriate Participant Information and Informed Consent Forms will be provided. The oral explanation to the participant will be performed by the Investigator or qualified delegated person, and must cover all the elements specified in the Participant Information Sheet and Consent Form.

2HG MR Spectroscopy in glioma  
Version 1.0 18.03.2024  
IRAS Project ID: 252870

The participant must be given every opportunity to clarify any points they do not understand and, if necessary, ask for more information. The participant must be given sufficient time to consider the information provided. It should be emphasised that the participant may withdraw their consent to participate at any time without loss of benefits to which they otherwise would be entitled.

The participant will be informed and agree to their medical records being inspected by regulatory authorities and representatives of the Sponsor(s).

The Investigator or delegated member of the study team and the participant will sign and date the Informed Consent Form(s) to confirm that consent has been obtained. The original will be signed in the Investigator Site File (ISF). The participant will receive a copy of the signed consent form and a copy will be filed in the participant's medical notes.

### **12.2.2 Study Site Staff**

The Investigator must be familiar with the protocol and the study requirements. It is the Investigator's responsibility to ensure that all staff assisting with the study are adequately informed about the protocol and their study related duties.

### **12.2.3 Data Recording**

The Principal Investigator is responsible for the quality of the data recorded in the CRF at each Investigator Site.

### **12.2.4 Investigator Documentation**

The Principal Investigator will ensure that the required documentation is available in local Investigator Site files (ISFs).

### **12.2.5 GCP Training**

For non-CTIMP (i.e. non-drug) studies all researchers are encouraged to undertake GCP training in order to understand the principles of GCP. This is not a mandatory requirement unless deemed so by the Sponsor. GCP training status for all investigators should be indicated in their respective CVs.

### **12.2.6 Data Protection Training**

All University of Edinburgh employed researchers and study staff will complete the [Data Protection Training](#) through Learn.

NHS Lothian employed researchers and study staff will comply with NHS Lothian mandatory Information Governance Data Protection training through LearnPro.

Non-NHS Lothian staff that have access to NHS Lothian systems will familiarise themselves and abide by all NHS Lothian IT policies, as well as employer policies

### **12.2.7 Information Security Training**

All University of Edinburgh employed researchers, students and study staff will complete the [Information Security Essentials modules](#) through Learn and will have read the [minimum and required reading](#) setting out ground rules to be complied with.

NHS Lothian employed researchers and study staff will comply with NHS Lothian mandatory Information Governance IT Security training through LearnPro.

Non-NHS Lothian staff that have access to NHS Lothian systems will familiarise themselves and abide by all NHS Lothian IT policies, as well as employer policies

### **12.2.8 Confidentiality**

All laboratory specimens, evaluation forms, reports, and other records must be identified in a manner designed to maintain participant confidentiality. All records must be kept in a secure storage area with limited access. Clinical information will not be released without the written permission of the participant. The Investigator and study site staff involved with this study may not disclose or use for any purpose

2HG MR Spectroscopy in glioma  
Version 1.0 18.03.2024  
IRAS Project ID: 252870

other than performance of the study, any data, record, or other unpublished information, which is confidential or identifiable, and has been disclosed to those individuals for the purpose of the study. Prior written agreement from the Sponsor or its designee must be obtained for the disclosure of any said confidential information to other parties.

### 12.2.9 Data Protection

All Investigators and study site staff involved with this study must comply with the requirements of the appropriate data protection legislation (including the General Data Protection Regulation and Data Protection Act) with regard to the collection, storage, processing and disclosure of personal information.

Computers used to collate the data will have limited access measures via user names and passwords.

Published results will not contain any personal data that could allow identification of individual participants.

Formatted: Indent: First line: 0 cm

## 13 STUDY CONDUCT RESPONSIBILITIES

### 13.1 PROTOCOL AMENDMENTS

Any changes in research activity, except those necessary to remove an apparent, immediate hazard to the participant in the case of an urgent safety measure, must be reviewed and approved by the Chief Investigator.

Proposed amendments will be submitted to the Sponsor for classification, review and authorisation.

Amendments to the protocol must be submitted in writing to the appropriate REC and local R&D for approval prior to implementation and prior to participants being enrolled into the amended protocol.

### 13.2 MANAGEMENT OF PROTOCOL NON COMPLIANCE

#### 13.2.1 Protocol Waivers

Prospective protocol deviations, i.e. protocol waivers, will not be approved by the Sponsors and therefore will not be implemented, except where necessary to eliminate an immediate hazard to study participants. If this necessitates a subsequent protocol amendment, this should be submitted to the REC and local R&D for review and approval if appropriate.

#### 13.2.2 Management of Deviations and Violations

Deviations and violations are non-compliance events discovered after the event has occurred. Protocol deviations will be recorded in a protocol deviation log and logs will be submitted to the Sponsors every 3 months. Each protocol violation will be reported to the Sponsor within 3 days of becoming aware of the violation.

Deviation logs will be maintained for each site in multi-centre studies.

Deviation logs/violation forms will be transmitted via email to [[contact]](mailto:[contact]). Only forms in a pdf format will be accepted by ACCORD via email. Forms may also be submitted by hand to the office. Where missing information has not been sent to ACCORD after an initial report, ACCORD will contact the Investigator and request the missing information. The Investigator must respond to these requests in a timely manner.

### 13.3 SERIOUS BREACH REQUIREMENTS

A serious breach is a breach which is likely to effect to a significant degree:

(a) the safety or physical or mental integrity of the participants of the study; or

(b) the scientific value of the study.

If a potential serious breach is identified by the Chief investigator, Principal Investigator or delegates, the Sponsor(s) ([[contact]](mailto:[contact])) must be notified within 24 hours. It is the responsibility of the Sponsor(s) to assess the impact of the breach on the scientific value of the study, to determine whether the incident constitutes a serious breach and report to research ethics committees as necessary.

### 13.4 STUDY RECORD RETENTION

All study documentation will be kept for a minimum of 3 years from the protocol defined end of study point. When the minimum retention period has elapsed, study documentation will be destroyed with permission from the Sponsor.

